6.6 EXPLORATORY EFFICACY ANALYSES

The efficacy endpoints will be summarized by treatment arm for each assessment time using summary tables, in terms of both absolute values and change from baseline.

Additional statistical modeling may be considered and will eventually be specified in the Statistical Analysis Plan (SAP).

6.7 EXPLORATORY PHARMACOKINETIC ANALYSES

The PK population will include all patients who received at least 1 dose of RO7234292 and had sufficient sampling to permit PK evaluation.

For patients in the PK population, CSF and plasma concentrations of RO7234292 will be presented descriptively, including arithmetic and geometric means, median, range, standard deviations, and coefficients of variation. Nonlinear mixed-effects modeling will be used to analyze the concentration–time data for RO7234292 in CSF and plasma following IT administration. A covariate analysis will be conducted to evaluate the effect of covariates such as body weight, age, and sex on RO7234292 exposure. Population and individual estimates of primary PK parameters (e.g., clearance, distribution volume) and secondary PK parameters (e.g., average trough plasma concentration) will be computed and used to explore the exposure-response relationship on selected endpoints, as well as safety measures. The data from this study may be pooled with data from other studies conducted with RO7234292 to support the population PK/PD modeling.

Details of this mixed-effects modeling and exploration of exposure-response analysis and results will be described and reported in a document separate from the Clinical Study Report.

6.8 EXPLORATORY IMMUNOGENICITY ANALYSES

The immunogenicity analysis population will consist of all patients with at least one ADA assessment. Patients will be grouped according to treatment received. The numbers and proportions of ADA-positive patients and ADA-negative patients at baseline (baseline prevalence) will be summarized by treatment group. For those who are ADA-positive, titers will be estimated, as well as antibody subtype. In addition, the numbers and proportions of ADA-positive patients and ADA-negative patients at baseline (baseline prevalence) and after drug administration (post-baseline incidence) will be summarized.

When determining post-baseline incidence, patients are considered to be ADA-positive if they are ADA-negative or have missing data at baseline but develop an ADA response following study drug exposure (treatment-induced ADA response), or if they are ADA-positive at baseline and the titer of one or more post-baseline samples is at least 4-fold greater than the titer of the baseline sample (treatment-enhanced ADA

response). Patients are considered to be ADA-negative if they are ADA-negative or have missing data at baseline and all post-baseline samples are negative, or if they are ADA-positive at baseline but do not have any post-baseline samples with a titer that is at least 4-fold greater than the titer of the baseline sample (treatment unaffected).

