2.4 EXPLORATORY IMMUNOGENICITY OBJECTIVES

The exploratory immunogenicity objectives for this study are as follows:

- To evaluate the immune response to RO7234292 on the basis of the following endpoints:
 - Incidence of anti-drug antibodies (ADAs) at specified timepoints relative to the prevalence of ADAs at baseline.
 - Determination of the ADA specificity followed by assessments of the magnitude (titer) of the ADA response.
- To evaluate potential effects of ADAs on the basis of the following endpoint:
 - Relationship between ADA status and efficacy, safety, or PK endpoints.

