3. STUDY DESIGN

3.1 DESCRIPTION OF THE STUDY

3.1.1 Overview of Study Design

This OLE study will evaluate the long-term safety and tolerability of RO7234292 administered IT to patients with HD. In addition, the study will obtain long-term data on the efficacy, immunogenicity, exposure, and biomarkers of RO7234292.

Effective 22 March 2021, dosing is paused, including enrollment. Patients already on the study will continue to be followed for safety and efficacy outcomes until study completion (see [Appendix 1a](#), [Appendix 1b](#), and [Appendix 2b](#)).

Only patients with prior enrollment in a Roche-sponsored or Genentech-sponsored study in HD for the RO7234292 development program that made provision for entry into an OLE study will be eligible for this OLE study. The preceding Roche-sponsored or Genentech-sponsored study must have been approved by the relevant national competent authority and applicable Institutional Review Board (IRB)/Ethics Committee (EC) in a country in order for a patient from that country to be included in the OLE.

For patients who have participated in previous Roche studies, entry into this long-term, open-label extension study will occur at an inclusion visit. This inclusion visit is a combined visit with the preceding study's last applicable visit where patients are due for their end of treatment visit, last CSF collection, or safety follow-up unless otherwise specified, and serves as the baseline visit for the long-term, open-label extension study. For participants who have not participated in a previous Roche study, a separate screening visit will occur to determine eligibility into the long-term, open-label extension study. Patients who successfully meet eligibility criteria will then enter the study and attend the baseline study visit. Patients who were enrolled in Study BN40423 before implementation of Version 4 of that protocol will be prematurely discontinued by the

Sponsor from Study BN40423 and offered treatment in this study (Study BN40955) when it is available at sites.

If dosing at the inclusion visit is not possible, the Medical Monitor should be consulted and a short treatment interruption may be permitted. For patients entering from Study BN40423 prior to implementation of Protocol Version 4, the inclusion visit should occur at the end-of-treatment visit for Study BN40423.

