For patients who did not previously receive treatment with RO7234292 (e.g., from a natural history study) or received short-term treatment (≤ 4 doses), the end of study visit for the preceding study will serve as the inclusion visit for Study BN40955. For patients who completed the full treatment course in the preceding study, the inclusion visit for Study BN40955 will take place at the visit at which the last dose was administered. For patients enrolled in Study BN40423 prior to implementation of Protocol Version 4 who were prematurely discontinued, the inclusion visit for Study BN40955 will take place at the end-of-treatment visit for Study BN40423. For patients entering from Study BN40697, in the event of any delay in start-up activities where it is not possible to conduct the inclusion visit for Study BN40955 at the time of last applicable visit in Study BN40697, a separate inclusion visit should be scheduled (see [Appendix 1a](#)). At the inclusion visit for Study BN40955, clinical ratings and assessments that are common between the preceding study and Study BN40955 will be completed once and will serve both studies. Clinical ratings and assessments required in Study BN40955 that were not completed as part of the preceding study will also need to be completed at the inclusion visit. Patients who were eligible for Study BN40423 (GENERATION-HD1) but were not randomized due to logistical challenges resulting from the COVID-19 pandemic will undergo screening and inclusion visits, see details of assessments in [Appendix 1b](#) and [Appendix 5](#).

Patients will undergo safety and tolerability evaluations that include neurologic examinations, vital signs, ECGs, clinical laboratory tests, Montreal Cognitive Assessment (MoCA), C-SSRS, neuroimaging assessments and reporting of AEs and concomitant medications, as detailed in [Appendix 1a](#) and [Appendix 1b](#). Patients enrolling from Study BN40697 will have an optional MRI of brain and spine with contrast media, in addition to the other brain neuroimaging assessments.

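### The Section 6.8 ADA rule, read with extension entry as baseline, can label drug-induced antibodies in previously exposed patients as treatment unaffected, and no split by prior exposure is planned

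*Combined protocol and SAP*

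**What the plan says.** **Rule.** Section 6.8 states: "When determining post-baseline incidence, patients are considered to be ADA-positive if they are ADA-negative or have missing data at baseline" and then develop a response (treatment-induced), or if they are positive at baseline and a later titer is at least four times the baseline titer (treatment-enhanced). Patients who are "ADA-positive at baseline but do not have any post-baseline samples with a titer that is at least 4-fold greater" than the baseline sample are counted ADA-negative and called treatment unaffected.

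**Reporting.** The population is everyone with at least one ADA assessment, grouped by treatment received. The numbers of ADA-positive and "ADA-negative patients at baseline (baseline prevalence) will be summarized by treatment group". Titers and antibody subtype are given for positives. Neither Section 6.8 nor any other part of Section 6 splits ADA results by prior exposure. Sections 6.6 and 6.9 defer possible further modeling to the SAP; Section 6.8 has no such sentence.

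**Endpoints (Section 2.4).** Under an objective about the immune response to RO7234292, the endpoint is "Incidence of anti-drug antibodies (ADAs) at specified timepoints relative to the prevalence of ADAs at baseline". A second endpoint is "Relationship between ADA status and efficacy, safety, or PK endpoints".

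**Baseline.** Section 6.8 does not say which sample is meant. Section 3.1.1 says the inclusion visit "serves as the baseline visit for the long-term, open-label extension study", and Section 4.5.2 also equates baseline with the inclusion visit. Appendix 1a schedules an immunogenicity sample at that visit, taken before dosing (footnote r).

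**Who enters (Section 3.1.1).** Where a full course was completed before entry, "the inclusion visit for Study BN40955 will take place at the visit at which the last dose was administered". In those from the earlier BN40423 protocol versions, "the inclusion visit for Study BN40955 will take place at the end-of-treatment visit for Study BN40423". Short-course patients and those from ML41885 have also been dosed. Prior placebo, natural-history and COVID-19-affected entrants have not.

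**The concern.** A rule built on induced, enhanced and unaffected responses suits patients whose baseline sample precedes any drug: positivity at baseline is then pre-existing reactivity, and unaffected means what it says. Here the baseline sample of many patients follows one or more doses. An antibody raised in the preceding study that persists at a stable titer is then reported as no effect of treatment. Incidence leaves out responses formed before entry, and baseline prevalence adds them to any pre-existing reactivity in naive patients.

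What is at stake is the reading of the immunogenicity tables against the Section 2.4 objective. If the Section 6.8 classes are also used for the relationship endpoint, drug-induced positives would sit in the ADA-negative comparison group and blur any association with efficacy, safety or PK.

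A smaller effect runs the other way. If the entry sample is missing, a carried-over antibody counts as newly induced. This should be uncommon, since the sample is scheduled at inclusion.

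**Working it through.** The plan gives no ADA rate, so there is no figure to reproduce. The check has four steps.

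**1. Apply the rule literally (titers invented for illustration).**

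| Entry | Later titers | Class for incidence |
|---|---|---|
| 160 | 160, 320 | negative, unaffected |
| 160 | 160, 80 | negative, unaffected |
| 160 | 640 | positive, enhanced |
| negative or missing | any positive | positive, induced |

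Nothing in the rule depends on whether the patient had drug before entry.

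**2. Share already exposed, August 2020 snapshot.** Sections 5.1.1 and 5.1.1.1 give counts with percentages, which fix the denominators:
- Extension: 30/22.9% gives 131 (Q8W); 11/15.1% gives 73 (Q16W); total 204.
- BN40697: 16/69.6% and 17/73.9% give 23 + 23 = 46 exposed.
- BN40423 original design cohort: 8/22.9% gives 35 (Q4W); 17/47.2% gives 36 (Q8W); 71 exposed.

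That is 46 + 71 = 117 exposed patients in these two sources. With assumed rollover r, the exposed share is f = r × 117/204: 57% at r = 1, 43% at 0.75 and 29% at 0.5. Full rollover is the upper limit for these two sources; short-course and ML41885 entrants are not counted.

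**3. What pooled prevalence leaves open.** Let p and q be entry positivity in naive and exposed patients, with q ≥ p ≥ 0. Pooled prevalence is P = (1 − f)p + fq, so the drug-induced excess is q − p = (P − p)/f, anywhere from 0 to P/f.

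| Assumed P | f = 57% | f = 43% | f = 29% |
|---|---|---|---|
| 6% | 0–10.5% | 0–13.9% | 0–20.9% |
| 1% | 0–1.7% | 0–2.3% | 0–3.5% |
| 0 | nil | nil | nil |

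At P = 6%, 0.06 × 204 = 12.2 patients are positive at entry. With a share b of them showing a 4-fold rise, 12.2 × (1 − b) are classed ADA-negative: 12.2, 9.8 or 6.1 for b = 0, 20% or 50%. How many of those labels are wrong depends on how much of the positivity is drug-induced, from none to all.

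**4. What the by-arm tables add.** Under Table 1, prior-Q8W patients (23 + 36 = 59) stay on Q8W and prior-Q4W patients (23 + 35 = 58) split about 29/29. At full rollover the exposed share is 88/131 = 67% in Q8W and 29/73 = 40% in Q16W.
- Nothing drug-induced: prevalence 6.0% in both arms.
- All drug-induced (q = 10.5%): 0.67 × 10.5% ≈ 7.0% in Q8W and 0.40 × 10.5% ≈ 4.2% in Q16W. A lower uniform rollover gives the same pair, because f falls as q rises.
- Incidence with assumed seroconversion s = 10% and b = 20%, equal in naive and exposed patients, is (1 − P)s + Pb. Pooled: 0.94 × 10% + 0.06 × 20% = 10.6% in either case. By arm when all is drug-induced: about 10.7% and 10.4%.

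So the two cases differ by about 7.0 − 4.2 = 2.8 percentage points in the arm contrast of prevalence. The standard error of that contrast at 6% is √[0.06 × 0.94 × (1/131 + 1/73)] ≈ 3.5 points.

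**The case against.** The strongest reply is that the analysis delivers its stated endpoint. Section 2.4 asks for incidence relative to baseline prevalence, an on-study increment, and Section 6.8 tabulates both, with titers and subtype. Entry-positive patients are visible. This stands, and it limits the point: what is lost is the ability to tell naive from exposed, not the patients themselves.

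Several stronger readings are tempting, and the documents do not support them:
- *Section 6.8 fixes extension entry as baseline.* It is silent. The reading rests on Sections 3.1.1 and 4.5.2. Section 2 permits linking earlier data but sets no ADA rule.
- *The planned tables would be identical whether none or all of the entry positivity is drug-induced.* They would not: prevalence is shown by treatment group and differs slightly between the two cases (step 4). Equal pooled incidence also rests on assuming the same seroconversion and boosting in naive and exposed patients. That is doubtful, since exposed entry-negatives have already had drug without remaining positive.
- *The arms are confounded in a known direction.* The snapshot suggests more exposure in Q8W, but later entrants on blinded Q8W and on Q16W each keep their regimen, so the final balance cannot be determined. No ADA test or decision is attached to the arms.
- *ADA status is undefined.* Section 6.8 defines post-baseline positive and negative in detail. What is missing is a statement of whether those classes serve the relationship endpoint.

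It is also fair to say that every ADA rate used here is assumed.

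**Conclusion.** The point holds in limited form. With the inclusion visit as baseline, the Section 6.8 rule can call a previously exposed, entry-positive patient treatment unaffected when the drug induced the antibody, and no planned table separates exposed from naive patients. The by-arm contrast does not make up for this. In the snapshot it is smaller than its standard error, reading it needs exposed shares by arm that Section 6 does not plan to report, and it would carry no information if the final shares were equal.

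The size is unknown. The ranges in the working depend on assumed entry positivity, boosting, seroconversion and rollover, and all shrink to nothing if entry positivity is near zero. The denominators of 204 and 117 are derived from reported percentages and describe August 2020, not the final population. Since the analysis is exploratory and descriptive, the priority is low to modest.

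**What to change.** In Section 6.8, state that the baseline sample is the pre-dose sample at the inclusion visit, and then:

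1. Report baseline prevalence and post-baseline incidence separately for RO7234292-naive patients (including prior placebo) and previously exposed patients, with treatment-induced and treatment-enhanced in separate rows. Derive exposure from preceding-study dose records, because one row of Table 1 merges untreated and short-course patients. For entrants from a study that is still blinded, fill it in after unblinding, as Section 4.2 requires.
2. Report previously exposed patients who are ADA-positive at entry without a 4-fold rise as their own category, not as treatment unaffected or ADA-negative. Keep them out of the ADA-negative group in the ADA-status relationship analyses.

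Optionally, as a sensitivity analysis, use the last ADA result before the first-ever dose as baseline where it exists and titers are comparable. This should not be the main analysis. BN40697 patients treated in the Phase I/IIa study had their first dose in a trial that Appendix 11 does not list, and the documents do not show whether usable results exist.

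The cost is wording, one stratification variable and some record linkage, which Section 2 allows. No new samples are needed. The downsides are smaller strata and a wait for unblinding in some patients.

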6.9 EXPLORATORY BIOMARKER ANALYSES

The biomarker endpoints will be summarized by treatment arm for each assessment time using summary tables, in terms of both absolute values and change from baseline.

Additional statistical modeling may be considered and will eventually be specified in the SAP.

6.10 HEALTH STATUS UTILITY ANALYSIS

The health status utility endpoints will be summarized using tables, listings, and graphs, as appropriate. Additional statistical modeling may be considered.

6.11 OPTIONAL INTERIM ANALYSES

The Sponsor may choose to conduct one or more interim analyses including safety, PK, PD biomarkers and clinical endpoints as relevant. Details of each interim analysis will be described in a dedicated SAP, which will be finalized before the conduct of the interim analysis.

7. DATA COLLECTION AND MANAGEMENT

7.1 DATA QUALITY ASSURANCE

The Sponsor will be responsible for data management of this study, including quality checking of the data. Data entered manually will be collected via EDC through use of eCRFs. Sites will be responsible for data entry into the EDC system. In the event of discrepant data, the Sponsor will request data clarification from the sites, which the sites will resolve electronically in the EDC system.

The Sponsor will produce an EDC Study Specification document that describes the quality checking to be performed on the data. Central laboratory data, electronic data from clinic visits (see Section 7.3) and electronic data obtained from the Roche HD mobile app (see Section 7.4) will be sent directly to the Sponsor, using the Sponsor's standard procedures to handle and process the electronic transfer of these data.

Electronic Case Report Forms and correction documentation will be maintained in the EDC system's audit trail. System backups for data stored by the Sponsor and records retention for the study data will be consistent with the Sponsor's standard procedures.

Patient-reported outcome, ClinRO, and PerfO data will be collected through the use of an electronic device provided by a vendor (see Section 7.3 for details).

7.2 ELECTRONIC CASE REPORT FORMS

Electronic Case Report Forms are to be completed through use of a Sponsor-designated EDC system. Sites will receive training and have access to a manual for appropriate eCRF completion. Electronic Case Report Forms will be submitted electronically to the Sponsor and should be handled in accordance with instructions from the Sponsor.

All eCRFs should be completed by designated, trained site staff.

Electronic Case Report Forms should be reviewed and electronically signed and dated by the investigator or a designee.

At the end of the study, the investigator will receive patient data for his or her site in a readable format that must be kept with the study records. Acknowledgement of receipt of the data is required.

7.3 ELECTRONIC PATIENT-REPORTED, CLINICIAN-REPORTED, AND PERFORMANCE OUTCOME DATA

An electronic device will be used to capture in-clinic PRO, ClinRO, and PerfO data. The device is designed for entry of data in a way that is attributable, secure, and accurate, in compliance with U.S. FDA regulations for electronic records (21 CFR Part 11). The data will be transmitted to a centralized database maintained by the electronic device vendor.

The electronic data will be available for view access only, via a secure vendor web portal. Only identified and trained users may view the data, and their actions will become part of the audit trail. The Sponsor will have view access only. System backups for data stored by the Sponsor and records retention for the study data will be consistent with the Sponsor's standard procedures.

Once the study is complete, the data, audit trail, and trial and system documentation will be archived. The investigator will receive patient data for the site in both human- and machine-readable formats on an archival-quality compact disc that must be kept with the study records as source data. Acknowledgement of receipt of the compact disc is required. In addition, the Sponsor will receive all data in a machine-readable format on a compact disc.

7.4 ELECTRONIC DATA OBTAINED BY THE ROCHE HD DIGITAL MOBILE APPLICATION

During "active tests" and "passive monitoring," the smartphone and wrist-worn wearable records movement and location data. Data on the technical status and connectivity of the devices is also recorded. Patients can choose to pause location data recording. No patient identifiable information is stored on the devices. For selected "active test" tasks, touch and sound is also recorded. Video is not recorded.

Roche HD mobile app (smartphone and wrist-worn wearable) sensor data are encrypted and uploaded to secure servers whenever the smartphone is connected to Wifi. All sensor data will be managed by the Sponsor who will monitor and ensure the integrity and quality of the acquired data. This includes, but is not limited to, the analysis of sensor data together with protocol-specified assessments and activities associated with routine daily living. The data will not be analyzed for efficacy until study end, unless they are chosen to be a part of a pre-specified interim analysis along with other clinical and/or biomarker endpoints.

7.5 SOURCE DATA DOCUMENTATION

Study monitors will perform ongoing source data verification and review to confirm that critical protocol data (i.e., source data) entered into the eCRFs by authorized site personnel are accurate, complete, and verifiable from source documents.

Source documents (paper or electronic) are those in which patient data are recorded and documented for the first time. They include, but are not limited to, hospital records, clinical and office charts, laboratory notes, memoranda, PROs, evaluation checklists, pharmacy dispensing records, recorded data from automated instruments, copies of transcriptions that are certified after verification as being accurate and complete, microfiche, photographic negatives, microfilm or magnetic media, X-rays, patient files, and records kept at pharmacies, laboratories, and medico-technical departments involved in a clinical trial.

Before study initiation, the types of source documents that are to be generated will be clearly defined in the Trial Monitoring Plan. This includes any protocol data to be entered directly into the eCRFs (i.e., no prior written or electronic record of the data) and considered source data.

Source documents that are required to verify the validity and completeness of data entered into the eCRFs must not be obliterated or destroyed and must be retained per the policy for retention of records described in Section [7.7](#).

To facilitate source data verification and review, the investigators and institutions must provide the Sponsor direct access to applicable source documents and reports for trial-related monitoring, Sponsor audits, and IRB/EC review. The study site must also allow inspection by applicable HAs.

